5.2.1 Inclusion Criteria

A subject will be eligible for study participation if he/she meets the following criteria:

1. Male or female, at least 18 years of age at time of screening.
2. Female who is:
 - practicing total abstinence from sexual intercourse (minimum 1 complete menstrual cycle)
 - sexually active with female partners only
 - not of childbearing potential, defined as:
 - postmenopausal for at least 2 years prior to screening (defined as amenorrheic for longer than 2 years, age appropriate, and confirmed by a follicle-stimulating hormone (FSH) level indicating a postmenopausal state), or
 - surgically sterile (defined as bilateral tubal ligation, bilateral oophorectomy or hysterectomy) or has a vasectomized partner(s);
 - of childbearing potential and sexually active with male partner(s):
 - currently using at least one effective method of birth control at the time of screening and
 - agree to practice two effective methods of birth control while receiving study drugs (as outlined in the subject information and consent form or other subject information documents), starting with Study Day 1 and for 30 days after stopping study drug or for 6 months after stopping study drug if receiving RBV (Note: Estrogen-containing hormonal contraceptives, including oral, injectable, implantable, patch and ring varieties, may not be used during study drug treatment).

3. Males who are not surgically sterile and are sexually active with female partner(s) of childbearing potential must agree to practice two effective forms of birth control (as outlined in the subject information and consent form or other subject information documents) throughout the course of the study, starting with Study

Day 1 and for 30 days after stopping study drug or for 6 months after stopping study drug if receiving RBV.

4. Chronic HCV infection prior to study enrollment. Chronic HCV infection is defined as one of the following:
 - Positive for anti-HCV Ab or HCV RNA > 1,000 IU/mL at least 6 months before Screening, and positive for HCV RNA and anti-HCV Ab at the time of Screening; or
 - HCV RNA > 1,000 IU/mL at the time of Screening with a liver biopsy consistent with chronic HCV infection (or a liver biopsy performed prior to enrollment with evidence of chronic hepatitis C disease).
5. Screening laboratory result indicating HCV genotype 1 infection.

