5.2.3.3 Prohibited Therapy

In addition to the medications listed in [Table 6](#), use of known strong inducers of CYP3A or strong inhibitors or inducers of CYP2C8 is prohibited within 2 weeks or 10 half-lives of the medication, whichever is longer, prior to the initial dose of study drugs and through the first 2 weeks after the subject has completed study drugs in the Treatment Period.

The investigator or a qualified designee should refer to the RBV labeling and DDI tool that will be provided by the sponsor for a list of prohibited medications. The site should document their DDI review in the source or print report and maintain it in the subject's study files. Anti-HCV medications other than those specified in the protocol will not be allowed during the Treatment Period of the study.

Subjects must be able to safely discontinue any prohibited medications. Subjects must be consented prior to discontinuing any prohibited medications for the purpose of meeting study inclusion criteria. During the Post-Treatment Period, investigators should reassess prohibited medications and subjects may resume previously prohibited medications or revert to pre-study doses, at a minimum of 2 weeks following discontinuation of study drugs, if applicable.

5.3 Efficacy and Safety Assessments/Variables**5.3.1 Efficacy and Safety Measurements Assessed and Flow Chart**

Table 7. Study Activities

Activity	Screening	Day 1 ^a	Week 2	Week 4	Week 12 ^b	End of Treatment (EOT) (Week 12 or 24) ^c or Treatment D/C ^{b,c}	Post-Treatment Wks 4, 12, 24, 52, 104, 156, 208, 260 or PT Treatment D/C
Informed Consent ^d	X						
Provide RBV Medication Guide ^e	X						
Medical History	X	X ^f					
Physical Exam ^g	X	X					
ECG	X						
Vital Signs, Weight and Height	X ^h	X	X	X	X	X	X
Pregnancy Test [serum (s) urine (u)] ⁱ	X (s)	X (u)		X (u)	X (u)	X (u)	X (u)
Hematology/Chemistry/Urinalysis/ Coagulation Panel	X	X	X	X	X	X	X ^j
FSH (all females)	X						
HBsAg, Anti-HCV Ab, Anti-HIV Ab	X						
HCV Genotype and Subtype	X						
IL28B Sample	X						
Child-Pugh Score ^k	X						
Liver ultrasound ^l	X					X	
Concomitant Medication Assessment ^m	X	X	X	X	X	X	X ⁿ

Table 7. Study Activities (Continued)

Activity	Screening	Day 1 ^a	Week 2	Week 4	Week 12 ^b	End of Treatment (EOT) (Week 12 or 24) ^c or Treatment D/C ^{b,c}	Post-Treatment Wks 4, 12, 24, 52, 104, 156, 208, 260 or PT Treatment D/C
Adverse Event Assessment	X	X	X	X	X	X	X ⁿ
Study Drugs Dispensation		X		X	X ^o		
Subject Care Plan Model ^p	X	X	X	X	X	X	X ^q

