HCV RNA Samples	X	X	X	X	X	X	X
Assignment of Subject Numbers via IRT	X						
Enrollment		X					
HCV Resistance Sample		X	X	X	X	X	X
Archive Samples (Plasma & Serum)	X	X	X	X	X	X	X
Study Drug Returned for IRT Reconciliation			X	X	X ^b		
Liver Biopsy, FibroScan or Fibro Test for liver fibrosis assessment ^r	X	X ^r				X ^r	
Patient Reported Outcome (SF-36v2 and FACIT-F) ^s		X		X	X	X	X
Assessment of Clinical Outcomes ^t			X	X	X	X	X
Clinical Assessment of Liver Decompensation ^k		X					
Total Insulin			X		X	X	X ^u

Wk = Week; D/C = Discontinuation; EOT (End of Treatment) = Final Treatment Visit; Day 1 = Baseline Visit

Table 7. Study Activities (Continued)

- a. All procedures to be performed prior to first dose.
- b. Treatment Duration Study Visits:
 - Subjects assigned to 12 weeks of treatment will complete the procedures and return drug from the screening visit through the EOT Week 12/ D/C visit procedures.
 - Subjects will complete EOT Week 12 visit procedures instead of completing a Week 12 visit.
 - Subjects assigned to 24 weeks of treatment will complete the procedures and return drug from the screening visit through the EOT Week 24/ D/C visit procedures at Week 24. Subjects will complete a Week 12 Study Visit as an interim visit.
 - Study drug returned for IRT Reconciliation at Week 24 is only applicable to subjects who will receive treatment for 24 weeks.
- c. Subjects that prematurely discontinue from the Treatment Period should return to the site to complete the Final/Treatment D/C visit procedures.
- d. Subjects will need to sign an informed consent for the study (prior to performing any screening or study-specific procedures).
- e. Where applicable/locally available.
- f. Medical history will be updated at the Day 1 Visit prior to study drug administration. This updated medical history will serve as the Baseline for clinical assessment.
- g. A symptom-directed physical examination may be performed at any other visit, when necessary
- h. Height will be measured at screening visit only.

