- i. Serum/Urine pregnancy testing is not required for female subjects with a documented history of bilateral tubal ligation, bilateral oophorectomy or hysterectomy or who are confirmed to be post-menopausal. A positive urine pregnancy test requires a confirmatory serum test. (Refer to Section 5.3.1.1) [Pregnancy Test] for additional details.) Females of childbearing potential who are receiving RBV should have urine pregnancy testing done monthly starting from Day 1 (Baseline) through 6 months after RBV discontinuation. Females of childbearing potential who are receiving DAA only should have urine pregnancy testing done thru Post-Treatment Week 4.
- j. Urinalysis will not be conducted after the Post-Treatment Week 4.
- k. Applies only to subjects with cirrhosis. The Child-Pugh score will be calculated in the EDC RAVE system. Subjects who were considered to be non-cirrhotic at the Screening visit but identified as cirrhotic (according to definitions listed in Section 5.1) during the screening period will return to the site prior to the baseline visit for Child-Pugh assessment.
- l. For subjects with compensated cirrhosis:
 - Subjects receiving 12 weeks of treatment will have a liver ultrasound performed at the screening visit and all Post-Treatment visits except Post-Treatment Week 4.
 - Subjects receiving 24 weeks of treatment will have a liver ultrasound performed at the screening visit, Week 24 visit, and all Post-Treatment visits except the Post-Treatment Week 4 and Post-Treatment Week 12.
 - Subjects with a historical negative liver ultrasound, CT or MRI (within 3 months prior to screening) are not required to undergo a screening ultrasound.

Table 7. Study Activities (Continued)

For subjects without cirrhosis: Liver ultrasound will be performed at the screening visit, Post-Treatment Week 52, Post-Treatment Week 156 and Post-Treatment Week 260. Subjects with a historical negative liver ultrasound, CT or MRI (within 3 months prior to screening) are not required to undergo a screening ultrasound.

- m. The DDI tool provided by the sponsor should be utilized to evaluate concomitant medications for potential drug-drug interaction (DDI).
- n. AEs and concomitant medications will not be collected after the Post-Treatment Week 4 visit. Only anti-HCV medications and concomitant medications relevant to SAE of death will be collected after the Post-Treatment Week 4 visit.

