Hemoglobin	Creatinine	Anti-HCV Ab ^b
Red Blood Cell (RBC) count	Total bilirubin ^{a,d}	Anti-HIV Ab ^b
White Blood Cell (WBC) count	Direct and indirect bilirubin	FSH (all females) ^b
Neutrophils	Serum glutamic-pyruvic transaminase (SGPT/ALT)	Urine and Serum
Bands, if detected	Serum glutamic-oxaloacetic transaminase (SGOT/AST)	Human Chorionic Gonadotropin (hCG) females) ^c
Lymphocytes	Alkaline phosphatase	HCV RNA
Monocytes	Sodium	IL28B ^b
Basophils	Potassium	HCV genotype and subtype ^b
Eosinophils	Calcium	Total Insulin
Platelet count (estimate not acceptable)	Inorganic phosphorus	
ANC	Uric acid	
Prothrombin Time/INR ^a	Cholesterol	
Activated partial thromboplastin time (aPTT)	Total protein	
Reticulocyte count	Glucose	
Urinalysis		
Specific gravity	Triglycerides	
Ketones	Albumin ^a	
pH	Chloride	
Protein	Bicarbonate	
Blood	Magnesium	
Glucose	Gamma-glutamyl transferase (GGT) ^d	
Urobilinogen	Creatinine clearance (Cockcroft Gault calculation)	
Bilirubin	Alpha2-macroglobulin ^d	
Leukocyte esterase	Haptoglobin ^d	
Microscopic (reflex)	Apolipoprotein A1 ^d	

- a. Also a component of the Child-Pugh Assessment.
- b. Performed only at Screening.
- c. Serum and urine pregnancy testing is not required for female subjects who are confirmed to be post-menopausal or who have a documented history of prior bilateral tubal ligation, bilateral oophorectomy or hysterectomy.
- d. Also a component of FibroTest.

Pregnancy Test

Serum and urine pregnancy tests are not required for female subjects with documented prior bilateral tubal ligation, bilateral oophorectomy or hysterectomy or for subjects who are confirmed to be postmenopausal.

Confirmation of postmenopausal status measured by FSH will be obtained at the Screening Visit only for all female subjects.

For females of childbearing potential:

- A serum pregnancy test will be performed at the Screening visit only and analyzed by the central laboratory.
- Pregnancy testing will be performed as specified in [Table 7](#) regardless of treatment regimen.
- Subjects that receive a RBV containing regimen will have pregnancy tests performed monthly throughout the Treatment Period and for a minimum of 6 months after the discontinuation of RBV, or according to the local RBV label and/or local treatment guidelines for RBV.

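### Criterion 2 counts a woman with a vasectomized partner as not of childbearing potential, which read literally drops her from between-visit monthly pregnancy tests on ribavirin

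*Protocol*

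**What the plan says.** Criterion 2 in Protocol Section 5.2.1, with the same wording in the synopsis, is the only definition of childbearing potential in the documents. Under the heading for women not of childbearing potential it lists menopause and then: "surgically sterile (defined as bilateral tubal ligation, bilateral oophorectomy or hysterectomy) or has a vasectomized partner(s". Women who are "practicing total abstinence from sexual intercourse (minimum 1 complete menstrual cycle", or who have only female partners, have separate lines outside that definition.

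Three places say who is excused from pregnancy testing:

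- Table 7, note i (Section 5.3.1): "Serum/Urine pregnancy testing is not required for female subjects with a documented history of bilateral tubal ligation, bilateral oophorectomy or hysterectomy", with confirmed menopause added.
- Table 8, note c (Section 5.3.1.1): "Serum and urine pregnancy testing is not required for female subjects who are confirmed to be post-menopausal", with the same three operations added.
- Section 5.3.1.1, Pregnancy Test: "Serum and urine pregnancy tests are not required for female subjects with documented prior bilateral tubal ligation, bilateral oophorectomy or hysterectomy", again with confirmed menopause.

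The monthly rule in Table 7 note i reads: "Females of childbearing potential who are receiving RBV should have urine pregnancy testing done monthly starting from Day 1". It runs to 6 months after RBV ends. The matching bullet in Section 5.3.1.1 stands under a heading that limits it to females of childbearing potential.

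**The concern.** A fertile woman whose only qualifying fact is her partner's vasectomy is defined out of childbearing potential, yet no exemption excuses her from testing. The two sets of rules therefore disagree about her. The monthly instruction depends on the defined term, so on a literal reading it does not reach her. A site that treats the exemption list as its working definition would test her monthly, and practice could differ across about 50 sites.

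The criterion is also uneven. Fertile women who are abstinent or have only female partners remain in monthly testing because their lines sit outside the definition. A fertile woman with a vasectomized male partner does not.

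The stakes are fetal exposure to RBV, whose teratogenicity is the protocol's own stated reason for criteria 2 and 3. Under Sections 5.4.1 and 6.6, a positive test on treatment, or the subject's own report of pregnancy, stops RBV at once. A missed test is therefore a missed chance to stop it.

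**Working it through.** The plan gives no figure to reproduce. The check sets the rules side by side and then counts tests.

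**Which rules reach her**

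| Rule | Limited by | Reaches her? |
|---|---|---|
| Table 7 row, "Pregnancy Test [serum (s) urine (u" | Only the exemption in note i | Yes: she is not exempt |
| Monthly RBV tests, Table 7 note i | Childbearing potential | No, by criterion 2 |
| Monthly RBV tests, Section 5.3.1.1 | Heading: childbearing potential | No, by criterion 2 |
| Three exemption lists | Three operations or menopause | No: she is not named |

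The visit tests stay and the between-visit tests fall away. Line indentation is not preserved in the text available, so the nesting in criterion 2 is read from its heading and its connecting words.

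**Inputs for the count**

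- Urine tests at visits (Table 7): Day 1, Week 4, Week 12, end of treatment (Week 12 or 24), and post-treatment (PT) Weeks 4, 12 and 24 within the 6-month window. The Week 2 visit has none.
- Day 1 procedures come before dosing (Table 7 note a): "All procedures to be performed prior to first dose". The end-of-treatment test comes as RBV ends. Neither can stop ongoing RBV.
- Assumption: monthly means every 4 weeks, from Day 1 to PT Week 24.

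**Count per RBV-treated woman**

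| | 12-week regimen | 24-week regimen |
|---|---|---|
| All monthly tests | 10 | 13 |
| Of these, at Table 7 visits | 6 | 7 |
| Monthly rule only | 10 − 6 = 4 | 13 − 7 = 6 |
| Tests that could stop RBV | Weeks 4, 8 | Weeks 4, 8, 12, 16, 20 |
| Of these, monthly rule only | Week 8: 1 of 2 | Weeks 8, 16, 20: 3 of 5 |
| Post-treatment, monthly rule only | PT Weeks 8, 16, 20: 3 of 6 | PT Weeks 8, 16, 20: 3 of 6 |

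The two lapsing groups add up: 1 + 3 = 4 and 3 + 3 = 6.

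**Gaps and added exposure**

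- Longest gap between visit tests on RBV: 12 − 4 = 8 weeks (12-week regimen) and 24 − 12 = 12 weeks (24-week regimen), against about 4 with monthly testing.
- A pregnancy that would first test positive at Week 8 on the 12-week regimen is found by testing at Week 12: up to 12 − 8 = 4 further weeks of RBV.
- One that would first test positive at Week 16 on the 24-week regimen is found by testing at Week 24: up to 24 − 16 = 8 further weeks.

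**Who can be affected**

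GT1a subjects and all subjects with cirrhosis receive RBV (Section 5.1.2). GT1b subjects without cirrhosis receive none and are outside the point. The 24-week column applies only to non-1b subjects with cirrhosis, within the F4 cap of 150 of about 600 subjects (150/600 = 25%). The documents do not say how many of these are fertile women with a vasectomized partner.

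**The case against.** The strongest objection is that the lapse depends on mixing two readings. In Section 5.3.1.1 the exempt women come first and the rules for females of childbearing potential follow, so a reader may take the second group to be everyone not exempt. She would then be tested monthly. If criterion 2 governs that heading instead, it also governs the bullet pointing to the Table 7 tests, and the visit tests should go too. This does not succeed. The Table 7 row stands on its own, limited only by note i's exemption, so it keeps her visit tests whichever way Section 5.3.1.1 is read. What stands is that a site may follow the exemption lists and lose nothing.

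Second, other safeguards exist. Section 5.2.3.2 asks subjects generally to use two contraceptive methods, Section 6.6 tells all subjects and partners to avoid pregnancy, a self-reported pregnancy stops RBV, and nurse educators are in contact several times a week. These lower the risk, and the added weeks of exposure need several unlikely steps. But the protocol requires monthly tests even of women using two methods and of abstinent women, so low risk is not its ground for omitting them.

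Third, the local RBV label, the RBV Medication Guide or the consent form may direct monthly tests. That is possible. Within the protocol, however, the reference to the local label sits in the same restricted bullet, so the text does not bring her back in.

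Fourth, it can be said that this is a wording matter with no bearing on the analysis. It has none on efficacy, but it concerns subject safety and is cheap to settle.

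**Conclusion.** The point holds. The only definition of childbearing potential places a fertile woman outside monthly RBV testing, while every exemption list implies that she should be tested. On the literal reading, with 4-weekly tests, she loses 1 of 2 (12-week regimen) or 3 of 5 (24-week regimen) of the tests that could stop RBV. She also loses 3 of 6 post-treatment tests. The latter cannot stop RBV; they serve detection during the 6 months for which Section 6.6 collects pregnancies.

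The conclusion rests on the literal reading of criterion 2 and on the 4-weekly assumption. Whether tests would be missed depends on how each site reads the text, and no estimate of the number of women or pregnancies is possible from the documents. Contraception is largely covered elsewhere. This is an inconsistency worth correcting for subject safety.

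**What to change.** In criterion 2 and in the synopsis, take the vasectomized-partner phrase out of the definition of women not of childbearing potential and give it its own eligibility line, beside abstinence and female-only partners. State in that line that the existing pregnancy-testing schedule applies, including monthly urine tests through 6 months after RBV for those who receive it. The definition then agrees with the exemption lists in Table 7 note i, Table 8 note c and Section 5.3.1.1. She stays eligible, because the lines of criterion 2 are alternatives. Section 5.2.3.2 already asks subjects for two contraceptive methods, so the move need not add a contraception requirement.

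The cost is a wording change in two places and at most 4 (12-week regimen) or 6 (24-week regimen) extra urine tests per affected RBV-treated woman. These can use the home kits that Section 5.3.1.1 already allows.

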5.2.2 Exclusion Criteria

A subject will be excluded from the study if he/she meets any of the following criteria:

1. Women who are pregnant or breastfeeding.

2. Positive test result for Hepatitis B surface antigen (HbsAg) or confirmed positive anti-HIV antibody (HIV Ab) test.
3. Use of medications listed below, or medications contraindicated for ritonavir or RBV (for those that receive RBV), within 2 weeks or 10 half-lives whichever is longer, prior to study drug administration including but not limited to:

Table 6. Medications Contraindicated for Use with the Study Drug Regimen

Alfuzosin	Estrogen-containing Medications for Systemic Use	Phenytoin
Astemizole	Fusidic Acid	Pimozide
Carbamazepine	Gemfibrozil	Rifampin
Dihydroergotamine	Lovastatin	Sildenafil*
Efavirenz	Methylergonovine	Simvastatin
Ergotamine	Midazolam (oral)	St. John's Wort
Ergonovine	Phenobarbital	Terfenadine
		Triazolam

Not all medications contraindicated with ritonavir and ribavirin are listed above. Refer to the most current package inserts or product labeling of ritonavir and ribavirin for a complete list of contraindicated medications.

* When used for the treatment of pulmonary arterial hypertension.

4. Use of known strong inducers of cytochrome P450 3A (CYP3A) or strong inducers of cytochrome P450 2C8 (CYP2C8) or strong inhibitors of CYP2C8 within 2 weeks of the respective medication/supplement, prior to initial dose of study drug.
5. Clinically significant abnormalities or co-morbidities, other than HCV infection that make the subject an unsuitable candidate for this study or treatment with RBV (if applicable) in the opinion of the investigator.
6. Current enrollment in another interventional clinical study, previous enrollment in this study, prior or current use of any investigational or commercially available anti-HCV agents other than IFN or RBV (including previous exposure to ABT-450, ABT-267 or ABT-333) or receipt of any investigational product within 6 weeks prior to study drug administration.

7. History of solid organ transplant.
8. Screening laboratory analyses showing any of the following abnormal laboratory results:
 - Creatinine Clearance (CrCl) < 30 mL/min as estimated by the Cockcroft-Gault equation:
$$\text{CrCl} = [(140 - \text{Age}) \times \text{Mass (in kg)} \times (0.85 \text{ if female})] / [72 \times \text{Serum creatinine (in mg/dL)}]$$
 - Albumin < 2.8 g/dL
 - Hemoglobin < LLN
 - Platelets < 25,000 cells per mm³
 - Total bilirubin > 3.0 mg/dL
9. Any current or past clinical evidence of Child-Pugh B or C Classification (Child-Pugh Score ≥ 7) or clinical history of liver decompensation such as ascites (noted on physical exam), variceal bleeding or hepatic encephalopathy.
10. Confirmed presence of hepatocellular carcinoma indicated on imaging techniques such as computed tomography (CT) scan or magnetic resonance imaging (MRI) within 3 months prior to Screening or on an ultrasound performed at Screening (a positive ultrasound result will be confirmed with CT scan or MRI).
11. HCV genotype performed during screening indicating infection with any genotype other than genotype 1.

Rationale for the Exclusion Criteria

- (1) The impact of AbbVie DAAs on pregnancies is unknown.
- (5, 7 – 10) To ensure safety of the subjects throughout the study.
- (3, 4, 6) To avoid bias for the evaluation of efficacy and safety by concomitant use of other medications.

(2, 11) To exclude subjects with viral infection other than HCV genotype 1.

